7.0 STUDY CALENDAR

	Screening	Baseline	ENCORE tx	Day 3	2 wk	4 wk	6 wk	3 mo	6 mo	12 mo	Extended F/U**
Informed consent	X										
Medical history	X										X
Pregnancy test	X										
Device interrogation (Standard of care)	X		X	X	X	X	X	X	X	X	X
24 Hour heart monitor* (Standard of care)	X						X	X	X	X	
SF-36 QoL		X					X		X	X	
12-lead EKG		X		X			X	X	X	X	
NIPS		X									
Cardiac CT + ECGI		X						X		X	
Cardiac MRI + PET		X		X				X			
Adverse events assessment		X	X	X	X	X	X	X	X	X	X
Blood work		X		X			X	X			

* For patients with PVC-induced cardiomyopathy-indications only

** Patients will be followed as per routine clinical practice, with data being collected from the medical record on outcomes for up to 5 years post-completion of study treatment. Device interrogation, 24 hour heart monitors, and imaging will be performed as clinically indicated but are not mandated by the protocol. Capture of AEs will be performed as described in Section 5.1.

8.0 DATA SUBMISSION SCHEDULE

Case report forms with appropriate source documentation will be completed according to the schedule listed in this section.

Case Report Form	Submission Schedule
Original Consent Form	Prior to registration
Registration Form Eligibility Form On-Study Form	Prior to starting treatment
ENCORE Form	Completion of last fraction of SBRT
Toxicity Form	6 weeks post-SBRT 3 months post-SBRT 6 months post-SBRT
QOL Form	Baseline 6 weeks post-SBRT 6 months post-SBRT 12 months post-SBRT
Follow-Up Form	6 weeks post-SBRT 3 months post-SBRT 6 months post-SBRT 12 months post-SBRT 2 years post-SBRT 3 years post-SBRT 4 years post-SBRT 5 years post-SBRT

9.0 MEASUREMENT OF EFFECT

1. Acute (≤ 90 days) safety of ENCORE will be defined as a $\leq 20\%$ rate of protocol-specific serious or serious adverse events (SAEs) using CTCAE v4.0 criteria that are possibly/probably/definitely related to study treatment, based on previously published data for expected invasive catheter-based VT-ablation procedures. Early stopping rules have been created such that if 5 or more patients develop ENCORE related SAEs out of the first 10 patients, this would be deemed significantly greater than 20% ($\alpha < 0.05$), and the trial will be halted.
2. Preliminary efficacy of ENCORE will be defined by the number of subjects with a reduction in ICD therapies (six month period before ENCORE treatment compared to six month period after ENCORE treatment) as adjudicated by continuous ICD monitoring.

10.0 DATA AND SAFETY MONITORING

In compliance with the Washington University Institutional Data and Safety Monitoring Plan, the Data and Safety Monitoring Committee (DSMC) will meet to review data semi-annually beginning six months after accrual has begun. The report will be prepared by the study statistician with assistance from the study team and will be reviewed by the DSMC, which will consist at minimum of a radiation oncologist, a cardiologist, and a statistician. The report will include:

- HRPO protocol number, protocol title, Principal Investigator name, data coordinator name, regulatory coordinator name, and statistician.
- Date of initial HRPO approval, date of most recent consent HRPO approval/revision, date of HRPO expiration, study status, and phase of study.
- History of study including summary of substantive amendments; summary of accrual suspensions including start/stop dates and reason; and summary of protocol exceptions, error, or breach of confidentiality including start/stop dates and reason.
- Study-wide target accrual and study-wide actual accrual.
- Protocol activation date.
- Average rate of accrual observed in year 1, year 2, and subsequent years
- Expected accrual end date
- Objectives of protocol with supporting data and list the number of participants who have met each objective.
- Measures of efficacy.
- Early stopping rules with supporting data and list the number of participants who have met the early stopping rules.
- Summary of toxicities
- Abstract submissions/publications
- Summary of any recent literature that may affect the safety or ethics of the study

The study principal investigator and Research Patient Coordinator will monitor for serious toxicities on an ongoing basis. Once the principal investigator or Research Patient Coordinator becomes aware of an adverse event, the AE will be reported to the HRPO according to institutional guidelines.

11.0 STATISTICAL CONSIDERATIONS

11.1 Early Stopping Criteria

Through a one sample test for proportions, assuming a maximal clinically acceptable SAE rate of 20%, 5 or more SAEs out of the first 10 patients would be significantly greater than 20% ($\alpha < 0.05$). As such, the protocol will be halted if 5 or more of the first 10 patients develop a SAE.

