11.2 Sample Size Justification

A total of 19 patients will be enrolled, which provides an optimal balance between assuring a high likelihood of safety (Phase I) with a preliminary assessment of efficacy (Phase II).

For the phase I component, the baseline rate of SAEs for catheter ablation is assumed to be 10-15%. Given the population being studied and a reasonable expectation that patients may be at a higher than typical risk of toxicity from any salvage therapy, we assume that SAE rates up to 20% would be clinically acceptable. Having said that, given that this is a totally noninvasive technique, it may well be that rates of toxicity are lower than that expected with catheter ablation. After exploring patient ranges from 15-25 patients, it was determined that 19 patients would provide a 75.4% power to detect an SAE rate about 20% (range, 5%-20%, $\alpha = 0.0829$).

For the phase II component, while some single institution series report much higher success rates, the baseline efficacy rate of catheter ablation in prospective trials ranges from 50-65%. As this is a salvage therapy in a high risk population, we assume that efficacy rates as low as 40% would be clinically acceptable. Using the 19 patient sample determined above, it was determined that 19 patients would provide 81.5% power to determine that ENCORE is not worse than 40% effective for the treatment of VT (range, 40-65%, $\alpha = 0.0885$).

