11.3 Analytic Plan for Primary Objectives

SAEs defined by CTCAE v4.0 criteria within 90 days of ENCORE that are possibly/probably/definitely related to study treatment will be recorded. ENCORE therapy will be deemed safe if the rate of SAEs is $\leq 20\%$. An additional early stopping rule dictates that if 5 or more out of the first 10 patients develop ENCORE related SAEs, the trial will be halted.

The number of ICD therapies delivered in the 6 month periods preceding and following ENCORE therapy will be recorded for each patient by interrogation of the ICD. ENCORE therapy will be deemed efficacious if there is a reduction in ICD therapies before and after treatment. The proportion of patients with efficacious ENCORE therapy will be calculated, with the intent of demonstrating at least 40% efficacy.

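### The only numerical safety boundary counts the first 10 patients, and no review is tied to the fourth affected patient, at which the 20% safety criterion can no longer be met

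*Combined protocol and SAP*

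**What the plan says.** The stopping rule appears in three places. Section 11.1 derives it from a one-sample test of a proportion, "assuming a maximal clinically acceptable SAE rate of 20" per cent. It states that "5 or more SAEs out of the first 10 patients would be significantly greater than 20" per cent and concludes that "the protocol will be halted if 5 or more of the first 10 patients develop a SAE". Section 11.3 restates it: "if 5 or more out of the first 10 patients develop ENCORE related SAEs, the trial will be halted". Section 9.0 also limits it to related events. Section 11.1 does not.

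Section 11.2 fixes the sample size: "A total of 19 patients will be enrolled". The final criterion is in section 11.3: "ENCORE therapy will be deemed safe if the rate of SAEs is" at most 20%, counting related events within 90 days.

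Section 10.0 says that the DSMC "will meet to review data semi-annually beginning six months after accrual has begun". Its report covers toxicities, the stopping rules with supporting data, and progress against each objective. The principal investigator and the coordinator watch for serious toxicity continuously. Section 5.7 adds prompt reporting of unanticipated problems to the IRB.

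**The concern.** The stopping rule and the final criterion do not connect. The rule looks at patients 1 to 10 only. The criterion looks at all 19 and is lost at the fourth affected patient, wherever that patient falls in the sequence. With 4 of the first 10 affected, the criterion has already failed and the rule has not fired. After that no count among the remaining nine patients can make it fire.

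This matters because acute safety is the phase I primary objective, section 1.7 says that safety has not been rigorously studied prospectively, and section 4.8 says that treatment cannot be discontinued once begun. Harm can then be limited only by a decision about the next patient, and the plan names no count at which that decision must be considered.

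**Working it through.** **Inputs.** Boundary 5 of 10 and reference rate 20% (11.1); N = 19 (11.2); criterion at most 20% (11.3). The true rates of 30, 40 and 50% are assumptions used to show a range. X is the number of affected patients, taken as binomial, with outcomes known at once.

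**1. The plan's own figure.** P(X ≥ 5 | 10, 0.20) = 0.0264 + 0.0055 + 0.0008 + 0.0001 = 0.0328, which is below 0.05. Four of 10 would give 0.1209. The normal approximation for 5 of 10 gives 0.0089, or 0.0241 with continuity correction. The rule is sound as a test whichever version was meant.

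**2. Where the criterion is lost.** 0.20 × 19 = 3.8, so at most 3 patients. 3/19 = 15.8% passes and 4/19 = 21.1% fails. The maximum is 3 for any evaluable number from 15 (0.20 × 15 = 3.0) to 19.

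**3. What the current rule catches.** Every halted trial has at least 5 affected patients. So P(at least 4 affected, no halt) = P(X ≥ 4 | 19) − P(X ≥ 5 | 10).

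| True rate | Halt, P(X ≥ 5 of 10) | P(X ≥ 4 of 19) | At least 4, no halt | Exactly 4 of first 10 |
|---|---|---|---|---|
| 20% | 0.033 | 0.545 | 0.512 | 0.088 |
| 30% | 0.150 | 0.867 | 0.717 | 0.200 |
| 40% | 0.367 | 0.977 | 0.610 | 0.251 |
| 50% | 0.623 | 0.998 | 0.375 | 0.205 |

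Given that a fourth affected patient occurs, about 4.8, 5.5, 5.3 and 4.2 further patients are treated on average at these four rates. The worst case is 19 − 4 = 15, when patients 1 to 4 are all affected and there is no fifth by patient 10.

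**4. Which cut-off section 11.2 used.** It says that "19 patients would provide a 75.4% power to detect an SAE rate about 20" per cent, with alpha 0.0829 and a range of 5 to 20%. P(X ≤ 1 | 19, 0.20) = 0.0144 + 0.0685 = 0.0829, and P(X ≤ 1 | 19, 0.05) = 0.3774 + 0.3774 = 0.755. Those figures belong to at most 1 of 19. With at most 3 of 19, the chance of declaring safety at a true 20% rate is 0.455. Under the 1-of-19 cut-off, safety is lost at the second affected patient, which happens with probability 1 − 0.0829 = 0.917 at a true 20% rate.

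**5. Extending the halting boundary.** Patient-by-patient binomial recursion, keeping 5 of 10:

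| Boundary after patient 10 | Halt at 20% | 30% | 40% | 50% |
|---|---|---|---|---|
| None (current) | 3.3% | 15% | 37% | 62% |
| Exact test at 0.05 after each patient: ≥ 6 at 11–14, ≥ 7 at 15–17, ≥ 8 at 18 | 6.4% | 29% | 61% | 86% |
| Calibrated: ≥ 7 at 11–15, ≥ 8 at 16–18 | 4.3% | 22% | 53% | 81% |

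The unadjusted version exceeds the 0.05 attached to the rule. Relative to the current rule it reduces the mean number treated by about 0.15, 0.6, 1.2 and 1.2 patients at the four rates. The calibrated version reduces it by under 0.1, then about 0.2, 0.5 and 0.7. At a true 30% rate, 65% of trials would still reach four affected patients without a halt under the calibrated version.

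**The case against.** A reader might infer that patients 11 to 19 have no protection and that the trial could run on with nobody asked to decide. The documents do not support that. A halt at 5 of 10 is what keeps patients 11 to 19 from being treated. Section 10.0 also provides a DSMC that includes a radiation oncologist, a cardiologist and a statistician, a toxicity summary, and continuous monitoring by the investigator. Its report has an entry for accrual suspensions. What is missing is a numerical trigger, not oversight.

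A reader might also infer that the section 11.1 test simply carries on after patient 10. The section does not say whether its test is exact, and the choice matters. For 5 of 11, an uncorrected z-test gives z = (0.4545 − 0.20)/√(0.16/11) = 2.11 and would halt, whereas the exact tail is 0.0504 and would not. Any later boundary is therefore a new design choice.

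The strongest defence is that losing a point-estimate criterion is not evidence of unacceptable harm. Four of 19 is 21%, the plan stops only on a rate significantly above 20%, and the phase II objective gives a reason to continue. This stands. It is why a fourth affected patient should prompt a review rather than a halt. It does not explain why nothing at all is tied to that point.

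**Conclusion.** The point holds as a gap in coverage, not an arithmetic error. Nine of 19 patients (47%) contribute no events to any numerical boundary, and no review is tied to the loss of the section 11.3 criterion. At a true 30% rate, 72% of trials would pass that point without a halt.

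The figures assume independent patients, one count per patient, all 19 enrolled unless halted, and outcomes known at once. The last is optimistic: the safety window is 90 days, the documents give no accrual rate, and they do not say whether accrual pauses while the first 10 are observed. A lag would reduce the number of patients spared by any rule, and for an added halting boundary that number is already only about 1 or fewer on average. The trigger of four depends on the section 11.3 reading. Under the cut-off that reproduces the section 11.2 alpha, the gap would open at the second affected patient.

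**What to change.** 1. Reconcile section 11.3 (at most 3 of 19) with the cut-off behind the alpha in section 11.2 (at most 1 of 19). The trigger count follows from that choice.
2. Keep 5 of 10. If the 20% criterion stands, add to sections 10.0 and 11.1: *An unscheduled DSMC review will be held when a fourth patient has a treatment-related SAE within 90 days. This review does not by itself halt the trial.*
3. Count patients, not events, and add the word *related* to section 11.1 to match sections 9.0 and 11.3.
4. Optional: if a halting boundary after patient 10 is also wanted, calibrate it so that the overall false-halt probability at a true 20% rate stays below 0.05. The last row of the second table is one example. Name the test used.

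The cost of items 2 and 3 is a few sentences and one unscheduled meeting, needed in about 54% of trials at a true 20% rate if all 19 are enrolled. Item 4 raises the false-halt probability from 3.3% to 4.3%.

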5.2 Serious Adverse Events (SAEs)

Definition: An adverse event that is any undesirable experience associated with the use of a medical product in a patient that results in death, hospitalization (new or prolonged), disability or permanent damage, or is life-threatening.

Specific to this protocol, SAEs are defined as AEs with CTCAE v4.0 grade 3 or higher resulting in hospitalization or grade 4-5 AE. Treatment-related SAEs were SAEs that are possibly, probably, or definitely related to protocol treatment.

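### Section 11.1 states the early stopping rule for any SAE, sections 9.0 and 11.3 state it for treatment-related SAEs, and the same data can halt the trial under one and not the others

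*Combined protocol and SAP*

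**What the plan says.** The stopping rule appears three times in the combined protocol and SAP.

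- Section 11.1 (Early Stopping Criteria): "the protocol will be halted if 5 or more of the first 10 patients develop a SAE". It has no attribution qualifier.
- Section 9.0 (Measurement of Effect): the trial is halted "if 5 or more patients develop ENCORE related SAEs out of the first 10 patients".
- Section 11.3 (Analytic Plan for Primary Objectives): "if 5 or more out of the first 10 patients develop ENCORE related SAEs, the trial will be halted".

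Section 5.2 separates the two terms. For this protocol, "SAEs are defined as AEs with CTCAE v4.0 grade 3 or higher resulting in hospitalization or grade 4-5 AE", with no condition on cause. It then adds a narrower class: "Treatment-related SAEs were SAEs that are possibly, probably, or definitely related to protocol treatment".

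The 20% limit comes from the primary safety endpoint in section 2.1, restated in 9.0. In both places it applies to SAEs at least possibly related to study treatment, within 90 days. Section 11.1 uses the same 20% as its reference rate.

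**The concern.** Read with the protocol's own definitions, 11.1 counts a wider set of events than 9.0 and 11.3. No passage says which section prevails.

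This is the only numerical rule for halting the trial, and unrelated SAEs are plausible in this population. Section 3.1 requires at least three VT episodes in six months, or a high PVC burden with cardiomyopathy. Section 5.1 describes heart failure progression as part of the expected natural history.

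Section 10.0 requires the monitoring committee's report to state how many participants have met the early stopping rules, and that number depends on which section is applied. If the question arose only once the counts were known, the event would be chosen with the data in view, which a prespecified boundary is meant to prevent.

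**Working it through.** **Inputs.** n = 10 patients; boundary 5 (sections 9.0, 11.1, 11.3); reference rate 20% and alpha below 0.05 (9.0, 11.1). Section 11.1 names the method: "Through a one sample test for proportions". X is the number of the first 10 patients with at least one counted event. Patients are taken as independent with a common rate p.

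**Step 1: reproduce the plan's figure.** P(X ≥ 5) = Σ C(10,k) p^k (1−p)^(10−k), for k = 5 to 10. At p = 0.20:

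- k = 5: 252 × 0.00032 × 0.32768 = 0.02642
- k = 6: 210 × 0.000064 × 0.4096 = 0.00551
- k = 7 to 10 together: 0.00086
- Sum: 0.0328

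This is below 0.05, as stated. A boundary of 4 gives 0.1209, so 5 is the smallest boundary that meets the stated alpha. The calculation uses only n, the boundary and p, so it holds for any counted event.

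**Step 2: the passages side by side.** Suppose 5 of the first 10 patients have an SAE as defined in 5.2, and 4 of those 5 have a related one.

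| Section | Event counted | Count | Decision |
|---|---|---|---|
| 11.1 | any SAE | 5 | halt |
| 9.0 | related SAE | 4 | continue |
| 11.3 | related SAE | 4 | continue |

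The reverse cannot happen. Every patient with a related SAE also has an SAE, so data that halt under 9.0 or 11.3 also halt under 11.1.

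**Step 3: halt probability by the rate of the counted event.** Same formula:

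| Patient-level rate | P(X ≥ 5 of 10) |
|---|---|
| 10% | 0.0016 |
| 15% | 0.0099 |
| 20% | 0.0328 |
| 25% | 0.0781 |
| 30% | 0.1503 |
| 40% | 0.3669 |
| 50% | 0.6230 |

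For related SAEs, 10% to 20% runs from the bottom of the catheter-ablation SAE range in 11.2 (10-15%) to the acceptable limit. For all-cause SAEs the documents give no figure, so 30% to 50% is an assumption.

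**Step 4: probability that the sections disagree.** Because related SAEs are a subset, P(11.1 halts and 9.0/11.3 do not) = P(any-SAE count ≥ 5) − P(related-SAE count ≥ 5). Differences are taken before rounding.

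| Assumed any-SAE rate | Related rate 10% | Related rate 20% |
|---|---|---|
| 30% | 0.1486 | 0.1175 |
| 40% | 0.3653 | 0.3341 |
| 50% | 0.6214 | 0.5903 |

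The disagreement shrinks to zero as the any-SAE rate approaches the related-SAE rate.

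**The case against.** The strongest reply is that 11.1 is shorthand. Section 11.3 first specifies related SAEs within 90 days, then calls ENCORE safe if the rate of plain SAEs is at most 20%. Section 11.2 also writes of SAE rates without a qualifier. Section 9.0 gives the same 5-of-10 rule, with the same 20% and alpha, for related events. This looks like one rule with a word missing once, and that is probably what was meant. But no passage says so, 5.2 gives the two terms different meanings, and a literal reading of 11.1 still yields a different decision.

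The gap may also be narrower than the tables suggest. Events only possibly related count as related under 5.2. Section 5.1 classes as treatment-related any acute heart failure worsening that needs new intravenous vasoactive drugs within six weeks. Some admissions that look unrelated would therefore count under all three sections.

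A reader might infer more than the documents support:

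- **That 11.1 governs because of its heading.** Nothing ranks it above 9.0 or 11.3, which also say the trial will be halted.
- **That the 20% and its alpha were derived for related SAEs as 5.2 defines them.** The revision history shows 5.2 was added by Amendment 2 and lists no change to section 11. The 0.0328 depends on no event definition.
- **That the test is invalid for all-cause SAEs.** It is valid for any count. The open question is whether 20% is a suitable reference for that count.
- **That 11.1 alone lacks a 90-day window.** None of the three stopping sentences states one. In 9.0 and 11.3 it appears only in the surrounding endpoint text.
- **That the one-year survival below 20% in section 1.7 supplies an all-cause rate.** It describes a broader group. Section 3.2 excludes patients judged unlikely to live 12 months in the absence of VT.

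**Conclusion.** The inconsistency is real and should be corrected. As written, the same data can halt the trial under 11.1 and let it continue under 9.0 and 11.3. It is a fault of wording in a decision rule: the boundary, its alpha, the sample size and the primary analysis are unaffected.

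Its direction is fixed. Followed literally, 11.1 can stop the trial when the related-SAE rule would not, but it cannot miss a related-SAE signal that the other sections would catch. A reader might take it as a gap in patient protection, and the subset relation rules that out.

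Its size is conditional. The 15% to 62% halt probabilities under 11.1 rest entirely on assumed all-cause rates of 30% to 50%. The comparison range of 0.2% to 3.3% assumes a related-SAE rate of 10% to 20%. That the sections disagree rests on the text alone and needs no assumed rate.

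**What to change.** Reconcile 11.1, 9.0 and 11.3 to one counted event. Wording 11.1 for ENCORE-related SAEs, with a reference to 5.2, would match 9.0, 11.3 and the primary safety endpoint in 2.1, to which the 20% limit is tied. The boundary and alpha would then stand unchanged.

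State in the same sentence whether the endpoint's 90-day window applies to the stopping count, and carry that into all three places.

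If all-cause SAEs are intended, change 9.0 and 11.3 instead, and justify 20% as the reference for that event or re-derive the reference and boundary.

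The first route costs one sentence in 11.1 and a clause on the window in each section, with no new data or patients. The second also needs a sourced all-cause reference rate.

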11.2 Sample Size Justification

A total of 19 patients will be enrolled, which provides an optimal balance between assuring a high likelihood of safety (Phase I) with a preliminary assessment of efficacy (Phase II).

For the phase I component, the baseline rate of SAEs for catheter ablation is assumed to be 10-15%. Given the population being studied and a reasonable expectation that patients may be at a higher than typical risk of toxicity from any salvage therapy, we assume that SAE rates up to 20% would be clinically acceptable. Having said that, given that this is a totally noninvasive technique, it may well be that rates of toxicity are lower than that expected with catheter ablation. After exploring patient ranges from 15-25 patients, it was determined that 19 patients would provide a 75.4% power to detect an SAE rate about 20% (range, 5%-20%, $\alpha = 0.0829$).

For the phase II component, while some single institution series report much higher success rates, the baseline efficacy rate of catheter ablation in prospective trials ranges from 50-65%. As this is a salvage therapy in a high risk population, we assume that efficacy rates as low as 40% would be clinically acceptable. Using the 19 patient sample determined above, it was determined that 19 patients would provide 81.5% power to determine that ENCORE is not worse than 40% effective for the treatment of VT (range, 40-65%, $\alpha = 0.0885$).

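### The power figures in section 11.2 are misdescribed (75.4% is the chance of concluding the SAE rate is below 20% if it is truly 5%) and do not belong to the success criteria in section 11.3

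*Combined protocol and SAP*

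**What the plan says.** Section 11.2 fixes the size of this single-arm study: "A total of 19 patients will be enrolled".

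**Safety, section 11.2.** The text gives a comparator figure: "the baseline rate of SAEs for catheter ablation is assumed to be 10-15"%. It cites "a reasonable expectation that patients may be at a higher than typical risk of toxicity from any salvage therapy" and sets the ceiling: "we assume that SAE rates up to 20% would be clinically acceptable". It adds that, because the technique is noninvasive, "it may well be that rates of toxicity are lower than that expected with catheter ablation". It then states the result: "19 patients would provide a 75.4% power to detect an SAE rate about 20% (range, 5%-20"%, alpha 0.0829.

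**Efficacy, section 11.2.** The comparator is again catheter ablation: "the baseline efficacy rate of catheter ablation in prospective trials ranges from 50-65"%. The floor follows: "we assume that efficacy rates as low as 40% would be clinically acceptable". The result is 81.5% power, with a printed range of 40-65% and alpha 0.0885.

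Neither paragraph gives a cut-off in patients, says which end of its range is the null and which the alternative, or gives power at any other rate.

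**Section 11.3.** ENCORE is to be called safe if the rate of treatment-related SAEs within 90 days is 20% or less; sections 2.1 and 9.0 use the same threshold. For efficacy, the proportion of patients with fewer ICD therapies is to be calculated, aiming to show at least 40%. No test, confidence limit or patient count is attached to either criterion.

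**The concern.** There are two problems.

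First, the safety sentence can be read as a roughly 75% chance of noticing an SAE rate of about 20%. An ethics board or the DSMC would find that reassuring. If the calculation instead gives the chance of a favourable conclusion under a low assumed rate, the sentence says something quite different about the primary safety objective.

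Second, alpha and power are properties of a decision rule. If the rule behind 11.2 is not the rule in 11.3, the reported error rates do not apply to the conclusions the trial will draw. At stake is how often a treatment sitting exactly at the unacceptable boundary (20% SAEs, or 40% efficacy) would be declared safe or effective.

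**Working it through.** **Inputs.** n = 19; safety boundary 20%; efficacy boundary 40%; printed ranges 5-20% and 40-65%; stated alpha/power 0.0829/75.4% and 0.0885/81.5% (all from 11.2). The criteria to compare are an observed SAE rate of at most 20% and efficacy of at least 40% (11.3). X is the number of the 19 patients with the event, taken as binomial(19, p).

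**Step 1: reproduce the safety figures.** For a rule of at most 1 of 19, P(X ≤ 1) = (1−p)^19 + 19·p·(1−p)^18.

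- p = 0.20: 0.0144 + 0.0685 = 0.0829, the stated alpha.
- p = 0.05: 0.3774 + 0.3774 = 0.7547 after rounding, the stated 75.4% apart from the last digit.

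Other low cut-offs do not give that alpha at p = 0.20: at most 0 gives 0.0144, at most 2 gives 0.2369, at most 3 gives 0.4551. A rule in the opposite direction, flagging an excess over 20%, does not give it either: 6 or more yields 0.1631 and 7 or more yields 0.0676. So the calculation is a test for a rate below 20%, with 5% as the alternative.

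**Step 2: reproduce the efficacy figures.** For at least 11 of 19, P(X ≥ 11) = Σ C(19,k)·p^k·(1−p)^(19−k), k = 11 to 19.

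- p = 0.40: 0.0885, the stated alpha.
- p = 0.65: 0.8145, the stated 81.5%.

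**Step 3: the same two rules at other rates.**

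| True SAE rate | P(X ≤ 1) |
|---|---|
| 5% | 75.5% |
| 10% | 42.0% |
| 15% | 19.9% |
| 20% | 8.3% (alpha) |

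| True efficacy | P(X ≥ 11) |
|---|---|
| 65% | 81.5% |
| 60% | 66.8% |
| 55% | 49.4% |
| 50% | 32.4% |
| 40% | 8.9% (alpha) |

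**Step 4: the section 11.3 criteria as counts.** 3/19 = 15.8% and 4/19 = 21.1%, so an observed SAE rate of 20% or less means at most 3 of 19. 7/19 = 36.8% and 8/19 = 42.1%, so an observed efficacy of 40% or more means at least 8 of 19.

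| True SAE rate | P(X ≤ 3) |
|---|---|
| 5% | 98.7% |
| 10% | 88.5% |
| 15% | 68.4% |
| 20% | 45.5% |

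| True efficacy | P(X ≥ 8) |
|---|---|
| 65% | 98.9% |
| 60% | 96.5% |
| 55% | 91.3% |
| 50% | 82.0% |
| 40% | 51.2% |

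**Step 5: the early stopping rule (11.1).** Halting requires 5 or more affected among the first 10. Any trial that halts has already exceeded both 1 and 3 affected patients, so the safety probabilities above are unchanged.

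**The case against.** **The arithmetic is right and the inputs are printed.** This stands. Both alpha/power pairs reproduce, and the ends of the printed ranges are the null and alternative that produce them. A reader might infer a computational error or a hidden assumption; the documents support neither. Choosing 5% and 65% is optimistic, and 5% has no figure or source behind it, but it is a choice of alternative. What fails is the description.

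**A reader might infer that the trial's real safety power is 42% to 20%, because 11.2 works from 10-15%.** The documents do not support that. The 10-15% is the catheter-ablation comparator, not a forecast for ENCORE. The remark about higher risk justifies the 20% ceiling, and the next sentence gives a qualitative reason why toxicity could be lower. The efficacy side is similar: the salvage-population remark justifies the 40% floor, and 11.2 also mentions single-institution series with higher success. Moreover, the comparator may not share ENCORE's endpoint. Section 1.2 reports VT recurrence of 35% in a meta-analysis and approaching 50% in observational studies, whose complements are 65% and 50%. That this is the source of the 50-65% is an inference. ENCORE counts any reduction in ICD therapies, which is easier to meet than freedom from recurrence.

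**A reader might also infer that the trial would probably fail even if ENCORE matched catheter ablation.** That does not follow from the stated criteria. Under 11.3, safety is declared with probability 88.5% at a true 10% and 68.4% at 15%. Read as an observed proportion, the efficacy target is met 82.0% of the time at a true 50%. The cut-offs of 1 and 11 appear nowhere in the documents; they are recovered from the stated alphas.

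This last objection limits the consequence but exposes the mismatch: the criteria are easy to meet because they carry far larger error rates than those 11.2 reports.

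**Conclusion.** The point holds as a misdescription and an internal mismatch. The 75.4% is the probability of concluding that the SAE rate is below 20% when it is truly 5%, using at most 1 of 19. It is not the chance of finding a rate near 20%. The 81.5% likewise applies only to at least 11 of 19 with a true rate of 65%.

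Neither pair describes section 11.3. For safety, the probability of a favourable conclusion at the 20% boundary is 45.5% under 11.3, against the 8.3% reported as alpha. For efficacy at the 40% boundary it is 51.2%, against 8.9%, if the target is an observed proportion. Section 11.3 does not settle that reading; if a formal test is intended, it must say so.

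The figures assume that all 19 patients are evaluable and independent, and that the SAE rate is the proportion of patients with at least one qualifying SAE. The conclusion says nothing about which SAE rate to expect with ENCORE, or whether the trial is likely to succeed. It deserves correction because it concerns both primary endpoints, but it does not call the sample size into question.

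**What to change.** In section 11.2:

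- Replace the detection wording with a statement that 75.5% (75.4% as printed) is the probability of concluding that the SAE rate is below 20% if the true rate is 5%.
- Label 5% and 65% as the assumed alternatives, and 20% and 40% as the null values.
- State each decision rule as a patient count with its alpha. For the rules behind the present figures, these are at most 1 of 19 (0.0829) and at least 11 of 19 (0.0885).
- Report power at SAE rates of 5/10/15% (75.5/42.0/19.9%) and efficacy rates of 50/55/60/65% (32.4/49.4/66.8/81.5%).

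Then reconcile 11.2 with 11.3, and with the same safety threshold in 2.1 and 9.0, so that the rule used for the conclusion is the one whose alpha and power are reported. Which rule to keep is for the sponsor. If the 11.3 criteria stay as observed proportions, 11.2 should carry the figures for at most 3 and at least 8 of 19, including the 45.5% and 51.2% at the boundaries.

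The cost is an edit to these sections, with no change in sample size. The downside is that the stated operating characteristics become less favourable either way: lower power away from 5% and 65% under one pair of rules, or a much higher chance of a favourable conclusion at the boundary under the other.
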